2.4 Data Management and Analysis

In this study, the primary objective is to analyze the effect of two independent factors: 1. Type of trocar system (AirSeal® trocar vs. standard trocars) 2. Intra-abdominal pressure (IAP: 10 vs. 15 mmHg) on the dependent factor: CO2 absorption. This will result in four (4) study arms. CO2 absorption in each arm will be compared at 15 and 60 minutes.

Justification of sample size: An effect size of 0.46 was calculated based on average CO2 absorption rates in a study comparing CO2 absorption when using the AirSeal® trocar versus standard trocars for laparoscopic renal surgery.¹ 30 patients per arm would be needed to detect an effect size of 0.46 or greater, with 80% power and a two-tailed alpha of 0.01. In order to allow for a possible 10% drop out, 132 patients will be enrolled in the study.

CO2 absorption calculation:

CO2 elimination rate = CO²³ absorption rate in order to keep patient metabolically constant.

¹ Wolf JS Jr, Monk TG, McDougall EM, et al. The extraperitoneal approach and subcutaneous emphysema are associated with greater absorption of carbon dioxide during laparoscopic renal surgery. J Urol. 1995;154:959-963.

² Ng CS, Gill IS, Sung GT, et al. Retroperitoneoscopic surgery is not associated with increased carbon dioxide absorption. J Urol. ³ 162:1268-1272

V3 022417

^{1,2}

$$\text{Carbon dioxide elimination rate} = \frac{ETCO_2 \times Vt \times RR}{(P_B - P_{H2O}) \times Wt}$$

ETCO₂: end-tidal carbon-dioxide pressure, Vt: expired tidal volume, RR: respiratory rate, P_B: barometric pressure (760 mmHg), P_{H2O}: partial pressure of water (13 mmHg), Wt: patient's weight in kilograms

General Analyses

Continuous variables will be summarized using means, standard deviations, medians, and ranges. If normally distributed, they will be analyzed using parametric tests such as T-test and analysis of variance. To find associations between continuous variables and to control by relevant covariates we will use multiple regressions. If the normality assumption is violated we will use non-parametric tests such as Mann-Whitney or Kruskal-Wallis.

[figure not shown]
Categorical variables will be summarized with frequencies and percentages and analyzed with logistic regression or categorical response models.

95% confidence intervals will be provided for descriptive statistics, as warranted.

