Subject characteristics are assumed to be comparable at the start of the study (randomization design) and so no formal statistical group comparisons will be conducted on the subject characteristics.

An overall alpha-level of 0.01 will be used as a cut-point for statistical significance and all statistical tests will be two-sided. All data will be analyzed by the Columbia University Mailman School of Public Health Biostatistics team.

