5.0 STUDY INSTRUMENTS: Questionnaires (See Appendix)

6.0 STUDY SUBJECTS

Any woman ≥ 18 years of age undergoing gynecologic laparoscopy with or without robotic assistance

6.1 Inclusion criteria:

Y Any woman ≥ 18 years of age undergoing a gynecologic laparoscopic procedure Y
Able to understand the consenting process and willing to participate in study

6.2 Exclusion criteria:

Y Patient unable to undergo laparoscopic procedure due to size of pathology or medical comorbidities Y
Emergent surgery

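### The primary outcome is indexed to body weight, but weight is not prespecified as a covariate in the primary comparison, so precision may be given away

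*Combined protocol and SAP*

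**What the plan says.** All references are to the combined protocol and SAP.

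- **Outcome (section 2.4, CO2 absorption calculation).** End-tidal CO2 × tidal volume × respiratory rate, divided by (barometric pressure minus water vapour pressure) × weight. The key ends "partial pressure of water (13 mmHg), Wt: patient's weight in kilograms".
- **Primary comparison (section 2.4).** Two factors, trocar type and intra-abdominal pressure: "This will result in four (4) study arms. CO2 absorption in each arm will be compared at 15 and 60 minutes". Hypotheses 1a and 1b in section 2.3 concern the trocar effect and the pressure effect.
- **Tests (section 2.4, General Analyses).** "If normally distributed, they will be analyzed using parametric tests such as T-test and analysis of variance"; otherwise Mann-Whitney or Kruskal-Wallis. One sentence allows multiple regression to control for relevant covariates. It lists none and is not tied to CO2 absorption.
- **Baseline (end of section 2.4).** "Subject characteristics are assumed to be comparable at the start of the study (randomization design"), with no formal group comparison planned.
- **Randomization (sections 2.1 and 3.0).** Simple; no stratification is stated.
- **Eligibility (section 6.1).** "Any woman ≥ 18 years of age undergoing a gynecologic laparoscopic procedure". Section 6.0 states no weight or BMI limit.
- **Sample size (section 2.4).** "30 patients per arm would be needed to detect an effect size of 0.46 or greater, with 80% power and a two-tailed alpha of 0.01".

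**The concern.** Dividing by weight removes the influence of weight only if CO2 elimination rises in exact proportion to it. The documents do not show or argue that it does. If elimination rises less than proportionally, the per-kg rate falls as weight rises, and two women with different weights get different outcome values for reasons unrelated to trocar or pressure. With no stated weight limit, the spread of weights could be wide.

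That variation sits in the error term of any unadjusted comparison, and the rank tests named as the fallback carry no covariate. What is at stake is the width of the interval, and so the power, of the primary comparison at a strict alpha of 0.01. A secondary point is that leaving the covariates unnamed leaves the choice open until the data are seen.

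**Working it through.** **1. The plan's own figure.** Section 2.4 does not say what kind of effect size 0.46 is ("An effect size of 0.46 was calculated based on average CO2 absorption rates in a study" is all it gives on the source). With a noncentral t calculation at two-sided alpha 0.01:
- Read as Cohen's f for two groups, d = 2 × 0.46 = 0.92. Power is 79.5% at 29 per arm and 81.2% at 30, so 30 per arm is reproduced.
- Read as Cohen's d, 113 per group are needed. Power is 20% at 30 v 30 and 46% at 60 v 60, so 30 per arm is not reproduced.
- Enrolment: 4 × 30 = 120, and 120 × 1.10 = 132, as stated.

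Both readings are carried forward.

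**2. Share of variance due to weight.** Let CO2 elimination be proportional to weight^b. The log per-kg rate then contains (b − 1) × log weight. With s² = ln(1 + CV²) for weight and residual SD r on the log scale (treated as the residual CV),

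R² = (1 − b)² s² / [(1 − b)² s² + r²].

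The documents give none of b, CV or r, so all three are assumptions. For weight CV 20% to 30%, s = 0.198 to 0.294:

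| b | r = 0.20 | r = 0.30 | r = 0.40 |
|---|---|---|---|
| 0.4 | 26–44% | 14–26% | 8–16% |
| 0.6 | 14–26% | 7–13% | 4–8% |
| 0.75 | 6–12% | 3–6% | 1.5–3% |
| 1 | 0 | 0 | 0 |

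Example: b = 0.6, CV 25%, r = 0.20 gives (0.4 × 0.246)² = 0.0097, and 0.0097 / (0.0097 + 0.04) = 0.20.

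**3. Effect on power.** Adjustment multiplies the standard error by √(1 − R²), which is 0.949 at R² = 0.10 and 0.894 at R² = 0.20. Power is therefore evaluated at d / √(1 − R²), with one degree of freedom fewer. The value d = 0.909 is the difference that has 80% power at 30 v 30.

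| Contrast | R² = 0 | 0.10 | 0.20 |
|---|---|---|---|
| 30 v 30, d = 0.909 | 80% | 85% | 89% |
| 60 v 60, d = 0.909 | 99.0% | 99.5% | 99.8% |
| 60 v 60, d = 0.46 | 46% | 52% | 58% |

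**4. Chance weight imbalance.** At weight CV 25%, one standard error of the difference in mean log weight is 0.246 × √(2/30) = 0.064 for 30 v 30. At b = 0.6 the outcome moves by (1 − 0.6) × 0.064 = 0.025, about 2.5%. With r = 0.20 the outcome SD is √(0.0097 + 0.04) = 0.223, so this is about 0.11 SD. For 60 v 60 the shift is 0.4 × 0.246 × √(2/60) = 0.018.

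**5. Type I error.** Simulation at alpha 0.01 (60 v 60, 4,000 runs per case; b = 0.5 and 0.75; weight CV 20% and 30%; r = 0.20) gave 0.009–0.012 unadjusted and 0.010–0.011 adjusted. The test is valid either way.

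**The case against.** - **The plan does not exclude weight.** A reader might infer that the arms will be compared with weight left out of the model. The documents do not say so: no primary model is specified, and regression on relevant covariates is allowed. Declining formal baseline tests is sound in a randomized trial and does not rule out adjustment. This stands; the gap is one of prespecification.
- **Chance imbalance is already covered.** A reader might infer that a weight difference between arms passes directly into the CO2 comparison as bias. The documents do not support that. Any shift is scaled by 1 − b, vanishes under proportionality, and is allowed for by randomization, as step 5 shows. Imbalance and added variance are the same precision cost, not two harms. This stands.
- **The size rests on outside assumptions.** Section 3.0 leaves ventilatory settings to the anesthesiologists, and those settings enter the outcome, so a residual CV above 20% is plausible. At 40% the weight share falls to about 1.5–16%. This stands, and it is why the range is wide.
- **The main effects gain little if the effect is large.** Hypotheses 1a and 1b are about 60 v 60 comparisons, which already have 99% power at d = 0.909. This stands for that reading. If 0.46 is Cohen's d, adjustment helps but leaves power well below 80%.
- **A log model is not required.** This stands: weight can be a covariate without logs, and logs turn the results into ratios.

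None of this removes the point that a variable built into the primary outcome is not named for adjustment.

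**Conclusion.** The point holds as a gap in prespecification with a cost in precision. Section 2.4 indexes the primary outcome to total body weight, leaves the primary model open and does not name weight as a covariate. There is no bias and no inflation of type I error.

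The size is uncertain. Under the assumed ranges the weight share runs from about 1.5% to 44%, and it is zero if elimination is proportional to weight. The power gain is useful for a pairwise 30 v 30 contrast at d = 0.909 or for a main effect at d = 0.46, and negligible for a main effect at d = 0.909. The change is worth making because it costs almost nothing even where the gain is nil. The conclusion does not depend on which reading of 0.46 is correct.

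**What to change.** In section 2.4, state that the primary analysis of CO2 absorption at each time point (15 and 60 minutes) is a linear model with trocar and pressure as factors and body weight as a prespecified covariate. Say that this takes precedence, for the primary outcome, over the general choice between parametric and rank tests. Keep the per-kg formula for reporting.

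One suitable form uses the log rate and log weight. Dividing by weight then only subtracts log weight from the response, so the weight slope changes by exactly 1 and the trocar and pressure contrasts are the same with or without indexing. The analysis therefore needs no assumption about b.

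Cost: a sentence or two in the plan, no new data, since the formula already requires weight, and one degree of freedom among about 120 patients. The small downside of the log form is that results are expressed as ratios.

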2.5 Graphical schema of study

3.0 STUDY PROCEDURES

- . / In the pre-operative area, subjects will be randomized via sealed, opaque envelopes containing a simple randomization scheme to one of the four groups:
 - Group A: Standard trocar/IAP 15 mmHg
 - Group B: Standard trocar/IAP 10 mmHg
 - Group C: AirSeal® trocar /IAP 15 mmHg
 - Group D: AirSeal® trocar /IAP 10 mmHg
- . / All intraoperative staff assigned to the patient will be made aware of her participation in the study. The delegated research staff will fill out all pre-operative data. (CRF1)
- . / Once in the operating room, standard surgical positioning, prepping and draping will be performed.
- . / The patient's randomization group will be stated at the surgical TIME OUT.
- . / Proposed surgery will commence using the AirSeal® or standard trocar at IAP of either 10 or 15 mmHg.
- . / All cases will be performed with routine general endotracheal anesthesia. Ventilatory parameters and settings will be at the discretion of the anesthesiologists.
- . / Pneumoperitoneum will be established using the Veress needle and trocar insertion performed at 20 mmHg.
- . / Immediately following trocar insertion/port placement, pressure will be decreased to 10 or 15 mmHg.
- . / If at any point the surgeon or anesthesiologist feels that the patient's safety is in question, necessary changes, including increasing the intra-abdominal pressure or switching between trocars, will be made expeditiously, and recorded.
- . / During surgery, "surgical data" and "anesthesia data" variables will be filled. (CRF 3 & 4)
- . / Following surgery 'General intraoperative data' variables listed below will be collected. (CRF 2)
- . / At the end of the case, the surgeon and the anesthesiologist will complete questionnaires (CRF 3 & 4)
- . / Post-operatively, the patient will fill out Visual Analog Scale pain scores at specified time periods. (CRF 5)
- . / PACU/nursing staff will fill out a questionnaire indicating pain medication used during recovery and post-operative recovery time (CRF 6)

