2.0 STUDY DESIGN AND STATISTICAL PROCEDURES

2.1 Overall design

Type of study: A randomized controlled trial

Randomization and blinding: Simple randomization

Single vs. multi-center: Single center

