2.3 Aims & Hypotheses

2.3a Specific Aim 1

To determine if there is a difference in CO2 absorption when gynecologic laparoscopy is performed using the AirSeal® valveless trocar system versus standard insufflation trocars at intra-abdominal pressures of 10 and 15mmHg

2.3a.1a Hypothesis 1a

CO2 absorption is decreased when gynecologic laparoscopy is performed using the AirSeal® valveless trocar system versus standard insufflation trocars

2.3a.1b Hypothesis 1b

CO2 absorption is decreased when gynecologic laparoscopy is performed at an intra-abdominal pressure of 10 versus 15 mmHg

2.3b Specific Aim 2

To determine if the anesthesiologists' perception of difficulty in maintaining adequate ETCO2 during gynecologic laparoscopy as measured on a 3-point likert scale differs using the AirSeal® valveless trocar system versus standard insufflation trocars at intra-abdominal pressures of 10 and 15mmHg

2.3b.1 Hypothesis 2

Maintaining adequate ETCO2 is less challenging when using the AirSeal® valveless trocar system versus standard insufflation trocars for gynecologic laparoscopy at intra-abdominal pressures of 10 and 15 mmHg

2.3c Specific Aim 3

To determine if the surgeon's visualization of the operative field during gynecologic laparoscopy as measured on a visual analog scale (VAS) differs when using the AirSeal® valveless trocar system versus standard insufflation trocars at intra-abdominal pressures of 10 and 15 mmHg

2.3c.1 Hypothesis 3

Visualization of the operative field is improved when using the AirSeal® valveless trocar system versus standard insufflation trocars for gynecologic laparoscopy at intra-abdominal pressures of 10 and 15 mmHg

2.3d Specific Aim 4

To determine if post-operative shoulder pain as measured on a VAS pain scale differs following gynecologic laparoscopy using the AirSeal® valveless trocar system versus standard insufflation trocars at intra-abdominal pressures of 10 and 15 mmHg

2.3d.1 Hypothesis 4

Post-operative shoulder pain is improved following gynecologic laparoscopy using the AirSeal® valveless trocar system versus standard insufflation trocars at intra-abdominal pressures of 10 and 15 mmHg

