8.0 INFORMED CONSENT PROCESS

After the provider determines eligibility of study participants, the informed consent process will be completed in 2 possible ways as listed/explained below by the PI or research staff (Co-investigator or other delegated study staff):

Option 1:

- . / Patient will be offered participation in the study at their pre-operative visit
- . / During this visit, the informed consent and HIPAA form will be explained and all questions answered
- . / The provider will inform the patient that participation in the study will be contingent on availability of the medical device on the day of the procedure
- . / The informed consent and HIPAA form will be signed by the patient and a copy given to them for their personal records
- . / The original 'wet-ink' signed consent and HIPAA form will be stored in the patient's chart
- . / On the procedure day, when the patient is in the pre-operative area, availability of the medical device will be confirmed and then the patient will be randomized into 1 of 4 groups
- . / Patients who are consented but not randomized will not be considered 'drop outs'

Option 2:

- . / At the time of the pre-operative visit, if time does not permit for consent to be obtained, the provider will obtain permission from the patient to allow a member of research team contact them about an ongoing research study – if the provider is not a Co-I in the study, he/she will document permission for the research team to contact the subject
- . / The patient will be given a copy of the informed consent and HIPAA form with their pre-operative packet and asked to review it in anticipation of a call (if they have agreed to this).
- . / A member of the research team will contact the patient to review the informed consent and HIPAA form and answer all questions
- . / Patient will be informed that participation in study will be contingent on availability of the medical device on the day of the procedure
- . / At the end of the phone conversation patient consent (or denial of consent) will be obtained and documented in patient's chart
- . / If the patient consents to participate by telephone, their signature will be obtained on the consent form in the preoperative area
- . / A copy of the signed form will be given to the patient and the original 'wet-ink' copy will be stored in the patient's chart
- . / When availability of the medical device is confirmed the patient will be randomized into 1 of 4 groups

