- . / Patients who are consented but not randomized will not be considered 'drop outs'

With both options of the informed consent process, when participation is offered to the patient, the informed consent and HIPAA form will be explained in detail along with the study design, procedures, inclusion/exclusion

criteria, risks and benefits, and study requirement. It will be emphasized that participation is completely voluntary and that she may revoke her participation at any time. There will be no further documentation of the informed consent process.

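### The plan gives no blinding status, allocates in the pre-operative area, and has no step to keep the arm from the woman who later scores her own shoulder pain

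*Combined protocol and SAP*

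**What the plan says.** The design summary in section 2.1 has a line that names blinding as a topic, but its only entry is the allocation method: "Randomization and blinding: Simple randomization".

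Section 3.0 gives the place and means of allocation: "In the pre-operative area, subjects will be randomized via sealed, opaque envelopes containing a simple randomization scheme". Section 8.0 agrees for consent Option 1, and under Option 2 it says "When availability of the medical device is confirmed the patient will be randomized into 1 of 4 groups". After positioning, prepping and draping, section 3.0 continues: "The patient's randomization group will be stated at the surgical TIME OUT". It does not say whether she is anaesthetised by then. All cases use general endotracheal anaesthesia, with ventilator settings left to the anaesthesiologist.

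On the outcome, section 3.0 says "Post-operatively, the patient will fill out Visual Analog Scale pain scores at specified time periods" (CRF 5). Hypothesis 4 in section 2.3 reads: "Post-operative shoulder pain is improved following gynecologic laparoscopy using the AirSeal® valveless trocar system versus standard insufflation trocars", at both pressures.

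On what she knows beforehand, section 8.0 has her told that "participation in the study will be contingent on availability of the medical device on the day of the procedure", and says that the consent form "will be explained in detail along with the study design, procedures" and other items.

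**The concern.** Sealed opaque envelopes conceal the arm until it is assigned. They do not blind anyone afterwards. Once the envelope is opened, three things matter for the pain score: whether she learns her arm, whether she expects one arm to hurt less, and whether she reports the score herself. The plan settles only the third.

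If some women learn that they had the new device and expect less pain from it, their scores may fall for that reason alone, in the direction Hypothesis 4 predicts. The analysis could not separate this from a real effect of the trocar. If practice varies between staff because nothing is written, a reader of the results also could not tell how many women knew.

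The patient is the one party who can readily be masked here. The surgeon and anaesthesiologist work with the assigned trocar and pressure and cannot be. Their knowledge has consequences of its own, which the plan does not acknowledge.

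**Working it through.** **Reading the sections together**

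| Question | What the text gives | What is left open |
|---|---|---|
| Blinding status (2.1) | Randomization method only | Open-label, single-blind or other |
| When and where allocated (3.0, 8.0) | Day of surgery, pre-operative area | Whether the envelope is opened in her sight or the result told to her |
| Announcement (3.0) | At the time out, listed after positioning, prepping and draping | Whether she is anaesthetised by then |
| What she has been told (8.0) | Study design explained; entry depends on the device being available | Whether she is told that less shoulder pain is expected with AirSeal |
| Who scores pain (3.0) | The woman herself, on a VAS | Whether she or recovery staff know the arm |

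No supplied section withholds the arm from her or from the recovery staff who complete CRF 6. No supplied section says that she is told.

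**How far it reaches**

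The patient's knowledge bears on objective c. It does not bear on the primary outcome, which section 2.4 calculates as ETCO2 × Vt × RR / [(P_B − P_H2O) × Wt]. The anaesthesiologist's knowledge is a different matter. That person hears the group announced and sets ventilation, which governs Vt and RR and influences ETCO2, the three varying terms in the numerator. The same person rates objective a, and the surgeon, who also knows the arm, rates objective b.

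**Illustrative size**

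The documents give no figure for the bias, so the shifts below are assumptions. They are average shifts over all AirSeal women, in SD units, with no true effect.

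- Evaluable women: the plan's enrolment reproduces as 30 × 4 = 120 and 120 × 1.10 = 132 (section 2.4). With 10% lost, 132 × 0.90 = 118.8, or 29.7 per arm.
- Test: AirSeal against standard trocar, two-sided alpha 0.01 (section 2.4), t distribution with 118.8 − 4 = 114.8 degrees of freedom, critical value 2.619.
- Noncentrality = shift × √(118.8 / 4) = shift × 5.450.

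| Average shift (SD) | Noncentrality | False-positive rate |
|---|---|---|
| 0 | 0 | 1.0% |
| 0.05 | 0.272 | 1.3% |
| 0.1 | 0.545 | 2.2% |
| 0.2 | 1.090 | 6.7% |
| 0.25 | 1.362 | 10.9% |
| 0.3 | 1.635 | 16.7% |
| 0.5 | 2.725 | 54.4% |

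These are averages over the group. If only half of the AirSeal women learned their arm, individual shifts of 0.1 to 0.5 SD would become average shifts of 0.05 to 0.25 SD, and the rate would run from 1.3% to 10.9%.

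**The case against.** The strongest reply is that no harm is shown. Allocation in the pre-operative area does not mean that the envelope is opened in front of the patient. The order of steps in section 3.0, with draping before the time out, suggests without proving that she is already asleep when the group is spoken. The consent pages, questionnaires and case report forms were not supplied and may contain an instruction. All of this stands. It limits the point to a missing safeguard.

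A reader might also infer that she expects AirSeal to hurt less, because she has had the study explained and knows entry depends on the device. The documents do not support that. Section 8.0 does not say she is told Hypothesis 4, and section 13.0 states that participants stand to gain no benefit, which weighs against an induced expectation. The route to bias stays open, but its strength is unknown.

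The upper false-positive rates, 54% in particular, should carry no weight. They come from assumed shifts with no source in the documents.

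Two further inferences fail. One is that missing blinding leaves the primary outcome untouched. That holds only for the patient's knowledge, not for the anaesthesiologist's. The other is that simple randomization or the enrolment figure is itself a defect. Simple randomization is defensible here, and 29.7 against 30 per arm costs about half a point of power: 0.807 against 0.812 for one pair of arms, at an assumed standardized difference of 0.92, the reading of the plan's 0.46 (as Cohen's f) under which 30 per arm reproduces.

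**Conclusion.** The point holds as a gap in conduct as well as in reporting. The plan raises blinding and leaves it unanswered, allocates before the operating-room steps, and has no supplied step to keep the arm from a woman who scores her own pain under a directional hypothesis. It affects one secondary outcome through the patient. A text that claims demonstrated bias, or that she knows her arm, would go further than the documents allow.

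The size is not derivable. The rates above show only that at alpha 0.01 a modest average shift would matter if it occurred. The conclusion rests on the supplied text, and an instruction in the missing forms would largely answer it. Separately, the plan should acknowledge that the anaesthesiologist and surgeon know the arm while setting ventilation and while rating objectives a and b.

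Priority is modest: worth doing because it is nearly free, not because the trial's main result depends on it.

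**What to change.** **Section 2.1.** Complete the blinding entry, for example: *Surgeons and anaesthesiologists are not blinded. The participant, and recovery staff where practicable, are not told the arm until her last pain score is recorded, unless her care requires it.* Add a sentence acknowledging that unblinded clinicians set the ventilation that enters the CO2 formula and give the ratings for objectives a and b.

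**Section 3.0.** After device availability is confirmed, open the envelope out of the woman's sight and do not tell her the result. State the group at the time out only once she is anaesthetised.

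**If this is not adopted,** describe the pain outcome as open-label and interpret it accordingly.

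**Section 2.4, at most.** Note that 132 less 10% leaves about 119 evaluable women, 29.7 per arm. No change to enrolment or to the randomization method is needed for this point.

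**Cost.** A few sentences and a small change in staff routine, with no new envelopes, visits or patients.
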